6.3 Day 2- Follow up Procedures

1. Research coordinator will call patient to ask if patient has experienced fever, shortness of breath, palpitations, headache or other symptoms. If any of the above have been experienced, investigator MD is immediately notified.
2. Investigator MD is notified of results by the research coordinator. MD will sign and date source document.
3. All pre-data analysis study data forms and consent are confirmed intact and in the study binder. Binder is kept in a secured file cabinet in the research coordinators office.

6.4 Schedule of Events

Study Activity	Day 0	Day 1	Day 2 (follow up)
Informed consent	X		
Medical records review. Confirm study inclusion criteria. Data recorded on source document.	X		
Subject eGFR determined. Labs obtained if Current serum creatinine is unavailable.	X		
Vital signs prior to and following imaging sessions recorded on source document (sitting blood pressure, respiratory rate, temperature, heart rate)		X	
Torso PET/MR fusion scan		X	
Pelvic mpMRI (SOC)		X	
Adverse event evaluation. Results recorded on source document.		X	
Follow-up call to collect adverse events. Result recorded on source document.			X

7 Statistical Plan

7.1 Sample Size Determination

Our null hypothesis is the hybrid C11-choline PET/MR and pelvic multiparametric MRI will have an equal accuracy of detecting patients with malignant lymph nodes in the very high risk/high risk prostate cancer patients compared to that in the conventional CT and bone scan method. With 20 patients, a McNemar's test with a 0.05 two-sided significance level will have 82% power to reject the null hypothesis if the difference in accuracy of the two methods is 0.3 or greater and assume discordant pairs is expected to be 0.31.

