1.1 Background

Prostate cancer is the most common solid cancer in men in the United States and the second most common cancer death in American men¹. Early and correct diagnosis of prostate cancer together with accurate staging is vital for appropriate clinical management strategy. To date, morphological and functional pelvic mpMRI and molecular imaging C11-choline PET have been playing vital roles in standard of care of prostate cancer.

Pelvic mpMRI, typically including T1-weighted, T2-weighted, diffusion-weighted imaging (DWI) and dynamic contrast-enhanced imaging (DCEI) with or without MR spectroscopic imaging (MRSI), is an established imaging modality and has been increasingly utilized for lesion detection and characterization, monitoring for active surveillance, detection of local recurrence in suspect cases, and MR guided intervention. In a prospective study of 70 consecutive patients with histopathologic correlation, the sensitivity, specificity, false-positive and false-negative rates, and the accuracy of mpMRI for extracapsular extension and seminal vesicle invasion have been reported to be 78.2% and 80%, 80.9% and 97%, 19.1% and 3.7%, 21.7% and 20%, 80% and 95.7%, respectively². However, the major limitation of pelvic mpMRI is the distant metastasis outside the field of view of prostate cancer.

Choline, a component of the phosphatidylcholines increased in prostate cancer, can be radiolabelled with either 11Carbon (C11-choline) and 18Fluoro (F11-choline). Unlike F18-fludeoxyglucose (FDG) tumoral uptake, which depends on increased cellular glycolytic pathway activity, choline uptake depends on active cell membrane synthesis, a metabolic pathway which more reliably reflects tumor metabolism in prostate cancer. C-11 choline PET has been shown to help identify sites of metastatic disease in men with biochemical recurrence after primary treatment failure. In the past decade, multiple investigations have demonstrated satisfactory sensitivity and specificity for the detection of recurrent PCa patients, and led to the FDA approval of C-11 choline production at Mayo Clinic 2012³⁻⁵.

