Additional effort has been taken to compare pelvic mpMRI and C11-choline PET in BCR PCa patients and demonstrated complimentary role of them for restaging prostatectomy patients with suspected recurrent disease. Kitajima K and colleagues compared the C11-choline PETCT with pelvic mpMRI with endorectal coil in detection of local recurrence, pelvic nodal metastasis and distant metastasis. They found that mpMRI is superior to C11-choline in detection of local recurrence; PET is superior for pelvic lymph node metastasis⁶.

The newly FDA approved hybrid GE SIGNA 3T PET/MR scanner provides an opportunity to investigate the clinical value of combined C11-PET/MR and pelvic mpMRI in primary prostate cancer. It is anticipated that the improved comprehensive imaging techniques may more

accurately stage untreated patients with high risk prostate cancer as well as better characterize the intra-parenchymal tumor. Therefore, we wish to determine the feasibility and efficacy (added value) of a hybrid, combined torso and focused C-11 choline PET/MR with pelvic mpMRI in characterizing and staging very high-risk and high-risk prostate cancer patients, which could provide a more accurate tumor characterization and staging information and lead to individualized precise treatment.

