1.5 Risks and Benefits

C-11 choline is involved in phosphorylation process integrated into phospholipids in the cell membrane as part of phosphatidylcholine, which is vital in prostate cancer cell. The main risk involves the exposure to the radioactivity associated with the C-11 isotope incorporation. This exposure has been calculated to be much lower than the F-18 FDG. In addition, there is no radiation risk related to MR scan. For MR safety concern, each subject will undergo MR safety screening performed by PET/MR technologist prior to imaging.

2 Study Objectives

Primary Objective:

- 1) Test whether a hybrid combination of focused C-11 choline PET/MR and pelvic mpMRI on a PET/MR system is feasible

Secondary Objective(s):

- 1) Determine the efficacy (added values) of a hybrid combination of molecular focused C-11 choline PET/MR and functional and anatomic pelvic mpMRI in comparison with clinical findings.
- 2) Determine the efficacy (added values) of a torso C-11 choline PET/MR in comparison with conventional CT and bone scan in depicting metastasis to lymph node and bone.

3 Study Design

This study will be a prospective study to test and optimize the feasibility of hybrid 3T PET/MR scan in diagnosing and staging high and very high risk prostate cancer patients.

The FDA approved C-11 choline PET tracer at a dose of 12-14 mCi will be administered intravenously prior to fused PET/MR scan, and prior to diagnostic pelvic mpMRI scan while patient lying in the scanner.

In addition, single dose of Gadavist® (Gadobutrol, Bayer) is at no more than 0.1 mmol/kg will be administered intravenously for pelvic mpMRI.

The whole imaging procedure will be conducted on an FDA approved GE SIGNA 3T PET/MR scanner.

The C11-choline PET/MR and pelvic mpMRI findings and results will be compared with serum PSA level, Gleason score, clinical CT and nuclear medicine whole body bone scintigraphy findings, and histopathological results obtained through standard of care management.

Our primary interest is to investigate the feasibility of hybrid C11-Choline PET/MR fusion and pelvic mpMRI in imaging primary prostate cancer.

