3.1 General Description

It is possible that improved comprehensive imaging techniques may more accurately stage untreated patients with high risk prostate cancer as well as better characterize the intra-parenchymal tumor. It is of interest to focus on potential synergy between molecular focused C-11 choline PET and functional and anatomic pelvic mpMRI. Therefore, we wish to determine the feasibility and efficacy (added value) of a hybrid, combination of torso and focused C-11 choline PET/MR with pelvic mpMRI on a clinical 3T PET/MR system in characterizing and staging very high-risk and high-risk prostate cancer patients, which could provide a more accurate tumor characterization and staging information and lead to individualized precise treatment.

3.2 Number of Subjects:

A total of twenty subjects will complete the study. Additional candidates may be screened to ensure completion of twenty subjects.

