* Axial T1-weighted LAVA-FLEX acquired in Part1. may be used for pre-contrast T1-weighted images.

Image review:

- PET/MR fusion study, including PET emission data, MRAC image and focused pelvis PET/MR fusion images will be sent to MIM Vista workstation for review by an independent, experienced board certified nuclear medicine radiologist without knowing clinical findings except for high risk prostate cancer.
- Focused mpMRI of pelvis images will be sent to PACS for review by an independent, experienced board certified body MR radiologist without knowing clinical findings except for high risk prostate cancer.

Evaluation of imaging findings:

Reviewers review images to evaluation imaging findings without knowing clinical findings except all subjects are recently diagnosed with very high-risk or high-risk prostate cancer. Readout workflow is illustrated in Figure 2. The scores will be recorded and stored in a secured REDCap file.

Pelvic mpMRI:

1. Lesion detection and characterization utilizing PI-RADS version 2 (15).
2. Tumor staging utilizing AJCC TNM staging system (3)
3. Detection of suspicious pelvic lymph nodes.
4. Detection of suspicious osseous lesion in the pelvis.

Torso and focused C-11 choline PET/MR:

1. Lesion detection and characterization.
2. Tumor staging
3. Detection of suspicious pelvic and extrapelvic lymph nodes.
4. Detection of suspicious osseous lesion in the pelvis and extrapelvic regions.
5. Document SUV in the region of interest (ROI) if possible.

Reference standards

[figure not shown]
[figure not shown]

1. Histopathology results when available
2. Clinical imaging study (CT, bone scan, etc).
3. Clinical follow-up (progression or regression at follow-up routine clinical imaging after treatment).

Prostate tumor localization and characterization: Focused C-11 choline PET/MR and pelvic mpMRI findings to be correlated with clinical prostate biopsy and surgery results.

Lymph node metastases: Torso and focused C-11 choline PET/MR and pelvic mpMRI findings to be correlated with clinical CT, lymph node biopsy, and surgery results

Bone metastases: Torso and focused C-11 choline PET/MR and pelvic mpMRI findings to be correlated with whole body bone scan, F-18 NaF PET/CT (if available), CT, dedicated MRI, and biopsy results.

Figure 1. Illustration of Part 1 “Torso C-11 Choline PET/MR” and Part 2 “Hybrid Focused C-11 Choline PET/MR and Pelvic mpMRI.”

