7.2 Statistical Methods

Descriptive Statistics

Descriptive statistics will be used to describe the average time of the total procedure, patients' tolerance and satisfaction level about the procedure. Paired t-test will be used to compare the suspicious lymph nodes and suspicious osseous lesions in the pelvis and extrapelvic regions detected by hybrid C11-choline PET/MR and pelvic multiparametric MRI method and by conventional CT and bone scan to investigate if the new method is able to detect more lymph nodes and osseous lesions compared to the conventional method. Paired t-test will also be used to compare the average SUV of lymph nodes and osseous lesions in the pelvis and extrapelvic regions by new method with that by conventional method to investigate if the new method provided more clarity in terms detecting the lymph nodes and lesions compared to the old method. If the patients' biopsy and surgery results available, sensitivity, specificity, positive predictive value and negative predictive value of detecting malignant lymph nodes and osseous lesions by the new method and by conventional method will be estimated and compared using McNemar's test.

Handling of Missing Data

As the sample size is 20 and imaging is completed over one day, no missing imaging data is anticipated.

Multiplicity

In current project, there is one primary objective and we don't have to adjust for multiple comparison.

Interim Analysis

There will not be interim analysis for the study.

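### Sections 7.1 and 7.2 compare PET/MR plus pelvic mpMRI only with CT and bone scan, so in the pelvis they cannot show what PET adds to standard-care mpMRI.

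*Combined protocol and SAP*

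**What the plan says.** Section 7.1 powers one contrast, a McNemar test of whether "hybrid C11-choline PET/MR and pelvic multiparametric MRI will have an equal accuracy of detecting patients with malignant lymph nodes" as CT and bone scan. Section 7.2 has three between-method comparisons: lesion counts, average SUV, and the set of sensitivity, specificity and predictive values. The first is of lesions "detected by hybrid C11-choline PET/MR and pelvic multiparametric MRI method and by conventional CT and bone scan"; the other two refer back to the same new and conventional methods.

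This fits the design statement in section 3, which says, for PET/MR as well, that "pelvic mpMRI findings and results will be compared with serum PSA level, Gleason score, clinical CT and nuclear medicine whole body bone scintigraphy findings", among other things.

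Secondary objective 2 (section 2) is to "Determine the efficacy (added values) of a torso C-11 choline PET/MR in comparison with conventional CT and bone scan", for nodes and bone. Secondary objective 1 asks for the added value of the hybrid combination against clinical findings. Section 3.1 adds: "It is of interest to focus on potential synergy between molecular focused C-11 choline PET and functional and anatomic pelvic mpMRI".

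Pelvic mpMRI belongs to the standard work-up: 4.1 requires it clinically, 4.2 says the research scan does not replace it, and 6.4 marks it as standard of care. Table 1 (section 3.3) lists it among the clinical exams beside focused PET/MR for the prostate, pelvic nodes and pelvic bone, and has separate pelvic and wider-torso or extrapelvic rows for nodes and bone. Section 3.4 plans accuracy measures for PET/MR, with no comparator.

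**The concern.** Patients receive mpMRI whether or not they receive the tracer. When mpMRI sits on one side of a comparison only, a pelvic gain over CT and bone scan mixes what mpMRI contributes with what choline PET contributes. A favourable result could be reported as added value of the new method when standard-care mpMRI supplied all of it.

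The protocol's own background makes the source of a gain an open question. In recurrent disease it reports that "mpMRI is superior to C11-choline in detection of local recurrence; PET is superior for pelvic lymph node metastasis". The synergy named in 3.1 cannot be assessed at all without a comparison that includes mpMRI alone.

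**Working it through.** **1. The plan's own figure.** Inputs from 7.1: n = 20, two-sided alpha 0.05, difference d = 0.30, discordant proportion q = 0.31. Miettinen approximation:

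power = Φ{[d√(nq) − 1.96q] / √[q² − d²(3 + q)/4]}

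- Numerator: 0.30 × √6.2 − 1.96 × 0.31 = 0.747 − 0.608 = 0.139.
- Denominator: √(0.0961 − 0.0745) = 0.147.
- Ratio 0.948, so power = 0.828. The stated 82% reproduces.

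**2. What that power depends on.** Only d and q enter, and both describe the combination against CT and bone scan. A gain of 0.30 is 0.30 × 20 = 6 patients. If those 6 are gained in pelvic nodes, the power is the same whether mpMRI supplies all, half or none of them. This holds by construction. It shows that the planned test carries no information on the split.

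**3. What the missing contrast would show.** The documents give no mpMRI share, so the splits are assumptions. Take 6 patients gained, no reverse discordance, and a reference standard in all 20. Combination versus mpMRI alone, Tango score 95% CI:

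| Source of the gain | Discordant pairs | Difference | 95% CI |
|---|---|---|---|
| All mpMRI | 0 vs 0 | 0.00 | -0.161 to 0.161 |
| Half each | 3 vs 0 | 0.15 | -0.035 to 0.360 |
| All PET | 6 vs 0 | 0.30 | 0.091 to 0.519 |

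For 0 vs 0 the limit is z²/(n + z²) = 3.84/23.84 = 0.161.

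Reverse discordance weakens this. At the same difference of 0.30, 7 vs 1 gives 0.027 to 0.537, and 8 vs 2 gives -0.011 to 0.555, which includes zero.

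**4. Precision for smaller differences.** Wald half-width = 1.96√[(q − d²)/n]; the reverse-discordant proportion is (q − d)/2. Assumed cases with reverse discordance present, where n = 10 stands for a reference standard in half the patients:

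| q | d | Reverse | n = 20 | n = 10 |
|---|---|---|---|---|
| 0.20 | 0.10 | 0.05 | 0.191 | 0.270 |
| 0.40 | 0.20 | 0.10 | 0.263 | 0.372 |
| 0.40 | 0.10 | 0.15 | 0.274 | 0.387 |

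The half-widths run from about 0.19 to 0.27 at n = 20 and from 0.27 to 0.39 at n = 10.

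**5. Where the problem stops.** Section 1.1 says that "the major limitation of pelvic mpMRI is the distant metastasis outside the field of view of prostate cancer". Outside the pelvis, then, the combination is in effect torso PET/MR, the index test of secondary objective 2. There the difference between 7.2 and that objective is mainly one of labelling.

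**The case against.** The strongest reply is that the layout already exists. Table 1 pairs focused PET/MR with pelvic mpMRI by site, with pathology as reference, and section 3.3 sends the two to separate blinded readers. That is right, and it rules out a stronger reading a reader might reach, that the plan ignores mpMRI or fails to collect the data. What is missing is an estimate in 7.2. Nor can one say that pelvic and extrapelvic findings are left unseparated: Table 1 has the rows, and 7.2 mentions both regions.

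Second, isolating PET is not a stated objective. The primary objective is feasibility, objective 2 names CT and bone scan, and 7.2 speaks of the new method, which is the combination. This has weight, and it is why the 7.1 test should stay. But objective 1 compares with clinical findings, which can include standard-care mpMRI, and 3.1 names the synergy outright.

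Third, Figure 2, which is not shown, may define how the reads are combined. It may, but a readout workflow would not supply an estimate.

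Fourth, 20 patients are few. That argues for estimation without a power claim, not for omitting the contrast.

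**Conclusion.** The point holds for the pelvis. Carried out as written, 7.1 and 7.2 cannot separate a pelvic gain due to PET from one due to mpMRI. The change is worth making because it is cheap. It does not undermine a pilot whose primary objective is feasibility.

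Three further inferences are not supported. The 7.1 comparison does not contradict the design, since section 3 describes the same comparison. Nothing here disputes the 82%. And the added contrast would not reliably settle the source of a gain. Under the assumed splits without reverse discordance, the intervals for the two extremes still overlap between 0.09 and 0.16, and with 8 vs 2 pairs even a 0.30 gain does not exclude zero.

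The conclusion about attribution rests on the text alone. The interval widths rest on the assumed splits, discordance and numbers with a reference standard.

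**What to change.** - **7.1:** keep the test. State that it and its 82% power concern the combined method versus CT and bone scan, and do not show the added value of PET.
- **7.2, main addition:** for pelvic nodes, pelvic bone and the prostate, following the Table 1 pairing, report the combination versus mpMRI alone as a descriptive paired difference. Give a 95% CI and the number of patients with a reference standard, and make no power claim. Use the separate blinded reads in 3.3 and the combining rule in Figure 2, or a prespecified rule if that figure gives none.
- **7.2, objective 2:** report PET/MR versus CT and bone scan by the Table 1 rows, pelvic and extrapelvic.
- **Labelling:** a PET/MR versus mpMRI comparison can only be supportive, because the PET/MR read itself carries MR information: "PET/MR fusion study, including PET emission data, MRAC image and focused pelvis PET/MR fusion images will be sent to MIM Vista workstation for review". For the torso, 3.3 names the MR sequences (Dixon and LAVA-FLEX); those behind the focused pelvic fusion images should be stated too.

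The cost is mainly wording, plus a combining rule if none exists. No new scan, patient or reader is needed. The downside is wide intervals, wider still where histology is missing.

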Objectives	1): Test whether a hybrid combination of focused C-11 choline PET/MR and pelvic mpMRI on a PET/MR system is feasible. 2): Determine the efficacy (added values) of a hybrid combination of molecular focused C-11 choline PET/MR and functional and anatomic pelvic mpMRI in comparison with clinical findings. 3): Determine the efficacy (added values) of a torso C-11 choline PET/MR in comparison with conventional CT and bone scan in depicting metastasis to lymph node and bone.
Number of Subjects	20
Diagnosis and Main Inclusion Criteria	Clinically diagnosed high and very high risk prostate cancer. Adult patients who are able to provide informed consent.
Study Product, Dose, Route, Regimen	C-11 choline PET tracer, One dose, totally 12-14 mCi, intravenous administration while patient is lying on the table
Duration of Administration	1 study day
Reference therapy	None
Statistical Methodology	Descriptive statistics will be used, including sensitivity, specificity, and accuracy, based on histopathological correlation.

1 Introduction

This document is a protocol for a human research study. This study will be carried out in accordance with the applicable United States government regulations and Mayo Clinic research policies and procedures.

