3.4 Primary Study Endpoints

Patient: Completion of all imaging examinations with laboratory results.

Data analysis:

Objective 1: Descriptive study. With biopsy and/or surgical histopathology as gold standard, the sensitivity, specificity and accuracy of PET/MR will be calculated.

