3.5 Secondary Study Endpoints

NONE

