4.4 Early Withdrawal of Subject

If a subject cannot finish the PET/MR imaging due to claustrophobia, he will be withdrawn. After PET/MR imaging, if a subject declines to undergo clinical evaluation and standard care of imaging, he will be withdrawn.

We plan to recruit a replacement subject in the event that a subject withdraws early to maintain the target number of 10 subjects.

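### Section 4.4 maintains 10 subjects where the rest of the plan has 20, and the 82% power in 7.1 assumes a nodal reference result for all 20 although Table 1 and 7.2 rely on pathology that may be missing

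*Combined protocol and SAP*

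**What the plan says.** **Number of subjects.** The Study Summary gives 20. Section 3.2 says "Additional candidates may be screened to ensure completion of twenty subjects". Section 7.1 bases its power on 20, and 7.2 repeats the number. Section 4.4 recruits replacements for early withdrawals "to maintain the target number of 10 subjects".

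**Power.** Section 7.1 tests equal per-patient accuracy for malignant lymph nodes, comparing hybrid C-11 choline PET/MR plus pelvic mpMRI with conventional CT and bone scan. A two-sided 0.05 McNemar test in 20 patients "will have 82% power to reject the null hypothesis if the difference in accuracy of the two methods is 0.3 or greater", with an expected discordant proportion of 0.31.

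**Reference standard for nodes.** The nodal rows of Table 1 in 3.3 list only pathology, with an availability qualifier. Section 7.2 makes the McNemar analysis conditional on patients having "biopsy and surgery results available, sensitivity, specificity, positive predictive value and negative predictive value of detecting malignant lymph nodes" and osseous lesions. The reference list in 3.3 is wider: it adds clinical imaging and clinical follow-up after treatment, and for nodes it sets clinical CT beside node biopsy and surgery.

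**Missing data.** Section 7.2 says "As the sample size is 20 and imaging is completed over one day, no missing imaging data is anticipated". It does not mention missing reference results. Section 7.3 analyses completers and does not require a reference result.

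**The concern.** Section 4.4 is the operative replacement rule. Read literally, it lets replacement stop at half the number on which the power rests.

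The 82% is the only reason 7.1 gives for 20 patients. An accuracy comparison can use only patients whose true nodal status is known. Eligibility requires clinical imaging but not nodal biopsy or surgery, and 4.4 does not replace patients who lack pathology. The evaluable number may therefore be below 20, and the plan does not allow for this.

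The wider list in 3.3 does not simply fill the gap. Baseline CT belongs to the method being compared. In any patient where CT decided the truth, CT would be right by construction, and a disagreement could only count against the new method. Section 3.3 does not say whether CT may decide alone.

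At stake is the reading of the nodal result. If it is not significant, it could be reported as coming from a test with 82% power when the power was lower. A significant or non-significant result that rested partly on CT as its own reference would also be hard to interpret.

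**Working it through.** **Inputs, all from 7.1.** n = 20; difference d = 0.30; discordant proportion ψ = 0.31; two-sided alpha 0.05 (z = 1.96).

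**What the inputs imply.** New method alone correct: (0.31 + 0.30)/2 = 0.305. Conventional method alone correct: (0.31 − 0.30)/2 = 0.005. Since ψ cannot be below d, its minimum is 0.30, and 0.31 is almost there. Conventional imaging is assumed to be right where the new method is wrong in 0.5% of patients.

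**Reproducing the 82%.**
- Wald: Φ(d√n/√(ψ − d²) − 1.96) = Φ(1.3416/0.4690 − 1.96) = Φ(0.900) = 81.6%.
- Miettinen: Φ((d√(nψ) − 1.96ψ)/√(ψ² − d²(3 + ψ)/4)) = Φ(0.1394/0.1471) = Φ(0.948) = 82.8%.
- Full enumeration of outcomes: uncorrected McNemar 85.0%, mid-p 74.0%, exact 56.9%.

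The stated figure reproduces.

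**Fewer evaluable patients, ψ = 0.31.** The documents give no verification rate, so these counts are assumptions.

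| Patients with a nodal reference | Wald | Miettinen | Uncorrected McNemar | Exact |
|---|---|---|---|---|
| 20 | 81.6% | 82.8% | 85.0% | 56.9% |
| 19 | 79.6% | 79.4% | 82.6% | 51.4% |
| 18 | 77.4% | 75.4% | 79.7% | 45.7% |
| 16 | 72.5% | 66.0% | 72.3% | 33.8% |
| 14 | 66.8% | 54.7% | 62.4% | 22.2% |

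**Higher discordance, n = 20, d = 0.30.** The plan gives no basis for 0.31, so these values are assumptions too.

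| ψ | Wald | Miettinen | Uncorrected McNemar |
|---|---|---|---|
| 0.33 | 78.2% | 74.9% | 77.7% |
| 0.35 | 74.9% | 69.0% | 71.6% |
| 0.40 | 67.4% | 58.8% | 60.3% |
| 0.50 | 55.4% | 47.0% | 47.2% |

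Both together, 16 patients and ψ = 0.40: 57.7%, 46.5% and 50.9%.

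**Matching 7.1 to the analysis.** Section 7.1 powers per-patient accuracy. The McNemar sentence in 7.2 covers sensitivity, specificity and predictive values, but not accuracy. Sensitivity uses node-positive patients only, so it has fewer pairs than the tables above. The index tests differ as well: 7.1 names hybrid PET/MR plus mpMRI, while secondary objective 2 in section 2 names torso PET/MR for the comparison with CT and bone scan.

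**The case against.** **This is a feasibility pilot.** Section 2 makes feasibility primary, and the Study Summary describes the statistics thus: "Descriptive statistics will be used, including sensitivity, specificity, and accuracy, based on histopathological correlation". That stands. The power figure does not bear on feasibility, which limits the weight of the point. But 7.1 does state a hypothesis and a power, and these should match the analysis.

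**The 10 in 4.4 is probably a leftover.** Very likely, since every other section that gives a number says 20. A reader might infer that the nodal test would be run on 10 patients; nothing in the documents suggests that. It still needs correcting, because 4.4 is the rule that staff would follow.

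**Section 3.3 supplies other references.** Follow-up on routine imaging after treatment could provide a reference for more patients, and its absence from the research schedule in 6.4 is no contradiction, because it is standard care. But Table 1 and 7.2 do not use it, no time window is given, and CT is not independent of the comparator. In Table 1 the availability qualifier may attach to surgery alone; the condition in 7.2 covers both biopsy and surgery.

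**The ranges depend on the formula.** They do. The plan names none, and another normal approximation (Connor) gives 70.3% two-sided at n = 20. The ranges over three methods are therefore illustrations and not bounds.

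**Section 3.4.** A reader might add its statement, "With biopsy and/or surgical histopathology as gold standard, the sensitivity, specificity and accuracy of PET/MR will be calculated", as evidence that nodal pathology may be missing, or that the CT comparison is also primary. It supports neither. It sits under Objective 1, concerns PET/MR alone, and mentions neither nodes nor limited availability. Section 2 makes the CT and bone scan comparison secondary. That "Secondary Study Endpoints" in 3.5 lists none is a labelling mismatch.

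**Conclusion.** The point holds. Section 4.4 contradicts four other places on the number of subjects. The 82% is sound arithmetic but conditional on two things that 7.1 does not present as conditions: a nodal reference result in all 20 patients, and discordance near its minimum. The plan makes no allowance for patients without nodal pathology, and the wider list in 3.3 lets part of the comparator serve as reference.

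Over Wald, Miettinen and uncorrected McNemar at discordance 0.31, power is 79-83% with 19 evaluable patients, 75-80% with 18, 66-73% with 16 and 55-67% with 14. With 20 patients and discordance 0.40 it is 59-67%. Mid-p and exact tests give less. All these cases rest on assumed verification and discordance.

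Two stronger readings fail. A reader might infer that the 82% is miscalculated; it reproduces. A reader might infer that it collapses unless all 20 are verified; losing one patient costs only about 2 to 3 points. The loss becomes material only with larger shortfalls or higher discordance. Naming the McNemar version and justifying 0.31 would be good practice, but their absence is missing detail and not a contradiction.

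**What to change.** 1. In 4.4, change 10 to 20.
2. In 7.1, state that 82% is conditional on 20 evaluable pairs and discordance 0.31. Restate power for the number expected to have a nodal reference result, over a range of discordance such as 0.31 to 0.50.
3. Reconcile 3.3 with Table 1 and 7.2 into one nodal reference standard. Exclude baseline CT as reference for the comparison with CT and bone scan. Say whether post-treatment follow-up counts and, if so, over what window. Report how many patients had each type of reference.
4. Add to the McNemar analysis in 7.2 the per-patient nodal accuracy comparison that 7.1 powers, as a secondary analysis. Reconcile the index test in 7.1 (hybrid PET/MR plus mpMRI) with that in secondary objective 2 (torso PET/MR).

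**Cost.** Wording and one small table. The stated power becomes less favourable and fewer patients may enter the nodal comparison. Limiting it to verified patients may bring partial-verification bias if biopsy or surgery depended on imaging; the report should say so. Restating the figure needs no extra patients. Keeping 20 evaluable pairs instead would need 20/0.75, or 27 patients, at an assumed 75% verification, and 20/0.50 = 40 at 50%.
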